For ctDNA testing in patients progressing on first-line anti-EGFR therapy, we currently use the CE-IVD cobas® EGFR Mutation Test v2 for the qualitative detection and identification of mutations in EGFR exons 18, 19, 20, and 21, including the T790M mutation. In this setting and with this method, we detect a EGFR mutation in ctDNA in 66.6% of the patients, which is in line with a large metaanalysis (Li et al, 2014) showing 65% sensitivity (95% confidence interval: 61-68%). In this pilot study, we intend to evaluate the feasibility of using the AVENIO ctDNA Expanded Kit, a NGS liquid biopsy tumor profiling assay for identifying genomic aberrations derived from solid tumors, in NSCLC patients progressing after first-line targeted treatment. This investigational test analyses 77 genes, including those currently in the NCCN Guidelines and emerging biomarkers relevant to clinical research.

Study objective(s)

The primary objective of this pilot study is to evaluate the overall sensitivity of the AVENIO ctDNA Expanded Kit to detect the primary molecular change in NSCLC patients progressing after first-line targeted treatment with an approved targeted therapy for those molecular subtypes of NSCLC.

The secondary objectives are:

- To describe the pattern of resistance mechanisms in patients with EGFR, BRAF, ALK, or ROS1-positive NSCLC who progressed after first-line treatment.
- To evaluate the rate of potential access to other approved or off-label targeted therapies.
- To evaluate the potential impact of this strategy to reduce the rate of rebiopsies in these patients, as compared with historical data from the year before.

2. Investigational material

Investigational material and comparator product(s)

The investigational assay to be used in this study is the AVENIO ctDNA Expanded Kit on a NextSeq 550 sequencer and the Oncology Analysis Server equipment, AVENIO software 2.0 and a report will be issued using NAVIFY Mutation Profiler software.

The comparator product in this study with be the routine use of the CE-IVD cobas® EGFR Mutation Test v2, which will be used in parallel in ctDNA from patients with EGFR-positive NSCLC in progression. We will use the 95% confidence interval values (61-68%; mean 65%) reported in the metaanalysis of Li et al (2014) as the cut-off points for assessing superiority (>68%), inferiority (<61%) or non-inferiority (61-68%).

3. Study population

Recruitment, enrollment

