100 patients will be recruited from all major cancer hospitals in Portugal over a planned recruitment period of 12 months.

period, and	
sample size	
Inclusion criteria	Adult patients with EGFR, BRAF, ALK, or ROS1-positive NSCLC who progressed after first-line treatment with an approved targeted therapy for those molecular subtypes of NSCLC who have not yet initiated second-line therapy.
Exclusion criteria	 Patients without EGFR, BRAF, ALK, or ROS1-positive NSCLC. Patients with EGFR, BRAF, ALK, or ROS1-positive NSCLC still responding to first-line treatment. Patients with EGFR, BRAF, ALK, or ROS1-positive NSCLC who progressed after first-line treatment and have initiated second-line therapy. Patients under the age of 18.
4. Study design and study procedure	
Study design	This will be an exploratory, multicenter, national, prospective, observational study.

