Subjects have the right to withdraw from the study at any time for any reason. If lost to follow-up, the assigned study staff will try to contact the subject by telephone followed by registered mail to establish and document as completely as possible the reason for the withdrawal. Subjects will be informed of circumstances under which their participation may be terminated by the responsible investigator without the subject's consent. The investigator may withdraw subjects from the study in the event of intercurrent illness, adverse events, lack of compliance with the study and/or study procedures (e.g., study visits), or any reason where it is felt that it is in the best interest of the subject to be terminated from the study. Any administrative or other reasons for withdrawal will be documented and explained to the subject. If the reason for removal of a subject from the study is an Adverse Event, the principal specific event will be recorded in the medical record.

5. Statistics

Primary and secondary endpoint(s)

To evaluate the overall sensitivity of the AVENIO ctDNA Expanded Kit to detect the primary molecular change in NSCLC patients progressing after first-line targeted treatment with an approved targeted therapy for those molecular subtypes of NSCLC.

The secondary endpoints are:

- Number of resistance mechanisms in patients with EGFR, BRAF, ALK, or ROS1-positive NSCLC who progressed after first-line treatment.
- The rate of potential access to other approved or off-label targeted therapies.
- The rate of rebiopsies in these patients, as compared with historical data from the year before.

Statistical methods

Not applicable as it is a pilot study.

Sample size, level of significance, and power

Not applicable as it is a pilot study. We will use the 95% confidence interval values (61-68%; mean 65%) reported in the metaanalysis of Li et al (2014) as the cut-off points for assessing superiority (>68%), inferiority (<61%) or non-inferiority (61-68%). If statistical power falls short after first 100 patients, cohort could be extended.

6. Safety assessment

Not applicable as it is an observational study. Treatment is not part of the protocol but done at physicians' decision, so safety assessment is not applicable.

7. Compliance Statements

General requirements: The study will be conducted in compliance to this study protocol, the current version of the Declaration of Helsinki, ICH GCP, and applicable local legal and regulatory requirements.

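### The cohort may be extended past 100 patients if power falls short, but the protocol defines no power, sets no maximum and does not limit the verdict to one assessment

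*Protocol*

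**What the plan says.** Protocol section 3 (Study population) fixes the size: "100 patients will be recruited from all major cancer hospitals in Portugal over a planned recruitment period of 12 months". It gives no derivation.

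Protocol section 5 (Statistics), under the heading on sample size, level of significance and power, opens with "Not applicable as it is a pilot study". The same paragraph takes the confidence limits of the cited meta-analysis "as the cut-off points for assessing superiority (>68%), inferiority (<61%) or non-inferiority (61-68"%). It closes with "If statistical power falls short after first 100 patients, cohort could be extended".

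The primary endpoint, in the same section, is a single proportion: "To evaluate the overall sensitivity of the AVENIO ctDNA Expanded Kit to detect the primary molecular change in NSCLC patients". The reference figure comes from the introduction, where the meta-analysis is cited as "showing 65% sensitivity (95% confidence interval: 61-68"%). The site's own experience with the comparator test is given beside it: "we detect a EGFR mutation in ctDNA in 66.6% of the patients".

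**The concern.** The paragraph contradicts itself. It says power does not apply, then makes continued enrolment depend on power. A shortfall can only be judged against a target, and none is set. After 100 patients the decision would rest on judgement, and nothing in the protocol says which information may inform it.

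Three restrictions that would make such an option harmless are absent: a maximum size, a decision made without knowledge of the detection rate, and a single application of the cut-offs. Without them, the study could look at 100, find the estimate at or below 68%, enrol more and look again. That would raise the chance of a false claim of superiority and push the reported sensitivity upward. It also leaves open how many patients the study may enrol, although section 3 gives a definite number.

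**Working it through.** **Can the trigger be evaluated?** No figure in the plan can be reproduced, because no significance level, power or alternative is stated. To see what 100 patients could mean, assume a two-sided 5% one-sample test with 80% power:

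N = [(1.960·√(p0(1−p0)) + 0.842·√(p1(1−p1))) / (p1−p0)]²

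Example with p0 = 0.68 and p1 = 0.80: (0.9143 + 0.3366)/0.12 = 10.42, and its square is 108.7, so N = 109.

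| True sensitivity p1 | N against 68% | N against 65% |
|---|---|---|
| 72% | 1044 | 352 |
| 75% | 334 | 169 |
| 78% | 160 | 98 |
| 80% | 109 | 72 |
| 85% | 52 | 39 |

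Depending on assumptions that the protocol does not make, 100 patients is ample or about a tenth of what is needed. The trigger therefore has no determinate meaning.

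**What could the sentence allow?** Inputs from the protocol: 100 patients; superiority above 68%; reference sensitivity 65%; the site's comparator rate of 66.6%. Assumptions: the cut-off is compared with the point estimate (the protocol does not say whether it is the estimate or a confidence limit); enrolment continues only if superiority has not been met; the same cut-off is then applied to the cumulative data without adjustment; extensions go to 150, or to 150 and then 200.

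An estimate above 68% requires at least 69/100, 103/150 or 137/200 detections. With X the cumulative number of detections and p the true sensitivity:

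P(superior) = P(X100 ≥ 69) + P(X100 ≤ 68, X150 ≥ 103) + P(X100 ≤ 68, X150 ≤ 102, X200 ≥ 137)

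The terms are exact, obtained by convolving binomial distributions. At p = 0.65 they are 0.2331, 0.0538 and 0.0283:

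- 100 only: 23.3%
- 100, then 150: 0.2331 + 0.0538 = 28.7%
- 100, 150, then 200: 0.2331 + 0.0538 + 0.0283 = 31.5%

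| True sensitivity | 100 only | 100, then 150 | 100, 150, then 200 | Single analysis at 150 | Single analysis at 200 |
|---|---|---|---|---|---|
| 65% | 23.3% | 28.7% | 31.5% | 19.7% | 16.8% |
| 66.6% | 34.7% | 42.8% | 47.3% | 32.9% | 31.3% |

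**Bias.** At a true 65%, the mean of the estimate at the point where the study stops is 65.5% with one extension to 150 and 65.8% with looks at 100, 150 and 200. The upward bias is about 0.5 to 0.8 points.

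**What belongs to the extension?** At a true 65% it adds 28.7 − 23.3 = 5.4 points (one extension) or 31.5 − 23.3 = 8.2 points (two). At 66.6% it adds 8.1 or 12.6 points. The 23.3% (or 34.7%) is present with no extension at all. It arises from comparing an estimate from 100 patients with a fixed cut-off, when the 95% half-width at 65% is 1.960·√(0.65·0.35/100) = 9.3 points.

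**The case against.** The strongest reply is that the sentence has an innocent reading. Section 3 admits four molecular subtypes. Under section 4 some institutions do not order the comparator test routinely, and in EGFR-positive patients the investigational assay runs on surplus sample. Too few evaluable results is an ordinary reason to enrol more patients and does not depend on outcome. An extension decided that way, with one verdict at the end, inflates nothing: at a true 65%, false superiority falls to 19.7% at 150 or 16.8% at 200. This stands. A reader might infer that the sentence instructs the investigators to extend whenever the result disappoints. It does not: it permits that and equally permits the harmless version. Nor does the protocol say that the cut-offs will be applied at 100 and again later.

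A reader might also infer that without a cap the inflation is unlimited. For the 68% cut-off and a true sensitivity below it, this is wrong, because the cumulative chance levels off: at a true 65%, looks every 50 patients up to 3000 give about 38%.

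The design label, "This will be an exploratory, multicenter, national, prospective, observational study", lowers the stakes, and no error rate is claimed. Section 7 also sends amendments that need ethical consideration for written approval. These points reduce the consequence but do not remove the defect, because the protocol itself sets superiority, inferiority and non-inferiority verdicts.

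The details of repeated looks are commonly left to an analysis plan, and one may exist. The defect here is different: the protocol states an extension rule whose trigger cannot be evaluated and whose size is open.

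**Conclusion.** The point holds as a defective stated rule. Section 5 contradicts itself on whether power applies. Its extension option has a trigger that cannot be assessed, no maximum, no blinding to the detection rate and no limit to a single verdict. A results-based extension is left open; it is not prescribed.

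If the option were used in that way, the added chance of false superiority would be about 5 to 8 points at a true 65% and about 8 to 13 points at the site's own 66.6%, with an upward bias of about 0.5 to 0.8 points at 65%. These sizes rest on assumed extensions to 150 and 200 and on reading the cut-off as applied to the point estimate. The contradiction and the missing limits rest on the text alone. The sponsor should correct the sentence; the pilot status makes this less than critical.

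**What to change.** Either delete the sentence and keep 100 patients, or replace it with:

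> Enrolment may be extended to at most N only if fewer than a stated number of patients have evaluable results for the primary endpoint; the decision is made without knowledge of NGS or cobas detection rates, and the verdict against the cut-offs is assessed once, at the end.

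The sponsor has to fill in N and the evaluable count. The change is one sentence. It keeps the legitimate reason for extending, and its only cost is the freedom to extend on the results.
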